3.3 Participants and Eligibility

The below table shows who will be recruited and consented.

Participants in study

	CHWs	Patients
--	------	----------

Initial Pilot Training	Up to $n = 25$	Up to $n = 75$
Stepped-Wedge Trial	Approximately $n = 60$	0

3.3.1 Initial Training

3.3.1a CHW Participants

CHW participants will be 25 CHWs from TB/HIV Care, Kheth’Impilo, Courage to Care, and ANOVA. CHWs from any of these NGOs will be eligible.

Rationale for enrolment numbers.

Based on previous trainings and interventions our team has piloted, we believe 25 CHWs will allow us to get a good sense of the preliminary acceptability, feasibility, and fidelity of the intervention and provide enough information to help us refine the training programme for future implementation.

Eligibility.

To be eligible for the training, CHWs must meet all of the following eligibility criteria: (1) be at least 18 years old; (2) previously completed CHW training approved by the Western Cape Department of Health; (3) be employed by one of the NGOs listed above as a CHW; (4) work with patients who have HIV and TB and struggle with depression or SU, or supervise CHWs who work with such patients; (5) be able to complete informed consent and study procedures in English, Afrikaans or isiXhosa; (6) be able to complete training in English.

3.3.1b Patient Participants

Patient participants will be up to 75 patients (up to three patients/ CHW) who receive care from a CHW who attended the training.

Rationale for enrolment numbers.

The number of patients ($n = 75$) was based on the number of CHWs in the study; each CHW will be asked to try to identify at least one and up to three patient who may be eligible for the study.

Eligibility.

To be eligible for the study, patients must meet the eligibility criteria below. These criteria were chosen to reflect patients with life experiences that are relevant to the content of the training programme. These criteria are identical to those used in our formative work.

Please note that the purpose of this pilot study is to focus on CHWs learning skills taught in the training/ the feasibility of the training, and not patient outcomes.

Patient Eligibility Criteria

Inclusion	Exclusion
1. Be a patient of one of the CHWs enrolled in the study	1. Currently pregnant (due to receiving more intensive adherence support and treatment plan)
2. Have or have had a history of TB/HIV co-infection	
3. The CHW believes the patient is struggling with substance use (alcohol or other drug use) or depression	2. Having multi-drug resistant TB (MDR- TB; due to receiving more intensive adherence support and treatment plan)
4. Age 18 or older	
5. Able to complete informed consent and study procedures in a language spoken by research team (isiXhosa, Afrikaans, or English)	

3.3.1 Stepped-Wedge Trial

3.3.2a CHW Participants

Participants will be 60 CHWs who are employed by one of the NGOs listed above. Please see Section 3.1.2 (above) for more information on these NGOs.

Rationale for enrolment numbers.

The number of CHWs to enroll ($N=60$) was determined through power calculations based on the primary effectiveness outcome (i.e., CHW stigma measured with the SDS).^{20,43,44}

A linear mixed model will be used for the primary outcome, considering both the within clinic correlation (i.e., multiple CHWs working at the same clinic) and the within person correlation (i.e., repeated measures on CHW stigma over time). In the power analysis, anticipated standardized effect sizes were defined from (1) a meta-analysis of 13 randomized clinical trials of mental health stigma reduction interventions that shows a standardized effect size of 0.63 on measures of stigma [121], and (2) prior work in sub-Saharan Africa using the SDS to test changes in mental health stigma among community mental health volunteers that had an effect size of 0.75.⁴⁴ Assuming similar baseline characteristics from a prior study using SDS among community health workers,⁴⁴ and an intra-class correlation of 0.1 within clinic and 0.3 within person, with 60 CHWs, our study can achieve a power of 86% at a significance level of 0.05 and a CHW training effect of 0.63, and 96% power at a training effect of 0.75.

A subset of these CHWs (up to $n=20$) will then participate in qualitative interviews. We will select CHWs for these further interviews by classifying CHWs based on level of change in stigma during the training. We intend to include CHWs who had reduced stigma following the training, no change in stigma following the training, and increased stigma following the training. We will also ensure that recruited CHWs represent the multiple NGOs that participated in the training. Only CHWs who attended the training will be eligible. We anticipate that this number of participants will allow us to reach theoretical saturation for qualitative analysis.⁴⁷

Eligibility.

To be eligible, CHWs must meet all of the criteria in the below table.

CHW Eligibility Criteria

Inclusion	Exclusion
1. At least 18 years old	1. Unable to complete informed consent or study procedures in English or isiXhosa
2. Be employed as a CHW through a partner NGO that provides HIV/TB CHW services	2. Unable to complete training in English
3. Work with patients who have HIV and TB and struggling with depression or SU	3. Participated in the initial trial(s) of this training.

3.3.2b Stakeholder participants

Participants will be up to n=28 NGO leaders as well as policymakers and other stakeholders working with these NGOs. Please see Section 3.1.2 (above) for more information on these NGOs.

Rationale for enrolment numbers.

This number of participants will allow us to represent a wide range of perspectives. As in Phase I of this study, we will identify stakeholders by asking health care system leadership to refer us to stakeholders involved in NGO-managed CHW services. NGO stakeholders that participated in formative work for this stepped-wedge training will be also be recruited. We anticipate this number will also allow us to reach theoretical saturation for qualitative analysis.⁴⁷

Eligibility

To be eligible, stakeholders must meet all of the criteria in the below table. Stakeholders that participated in formative work for this stepped-wedge training will be eligible to be enrolled, however prior participation is not required.

Stakeholder Eligibility Criteria

Inclusion	Exclusion
4. At least 18 years old	1. Unable to complete informed consent or study procedures in English or isiXhosa
5. Be employed by or referred by a partner NGO that provides HIV/TB CHW services	2. Unable to complete training in English
6. Work with patients who have HIV and TB and struggling with depression or SU	

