3.2.2 Stepped-Wedge Trial

We will use a stepped-wedge design.

CHWs will be clustered based on the site at which they work. When recruiting participants, we will aim to recruit approximately 20 CHWs per cluster.

CHWs across all clusters will be recruited and complete a baseline assessment at approximately the same time. In stepped-wedge trials, all groups have different intervals of a baseline period in which they are not exposed to an intervention (which we refer to as “treatment as usual” or “TAU”). Following this, at measurable intervals (steps), one group at a time will receive the training intervention. This process continues until all clusters have received the intervention. Then, at least one more follow-up assessment occurs after all clusters have received the intervention.

In this study, when a cluster receives the intervention (versus continues TAU) depends on whether they are randomized to Training Time #1, Training Time #2, or Training Time #3. Each training time will occur at a measurable intervention (compared to when the baseline assessment was conducted) so that the doses of TAU are discernable.

During data analysis, outcome variables will be compared between people before taking the intervention (TAU only; timepoints are baseline assessment (t1) and pre-training assessment (t2)) and with the same group of people after the intervention (TAU+Training; additional timepoints are 3-month follow-up (t3) and 6-month follow-up (t4) after adjusting for individual random effect and time effect.

Randomization will not affect any other TB/HIV-related clinic services or mental health training.

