3.5.2 Stepped Wedge Trial

3.5.2a CHW Screening & Consent

Potentially eligible CHWs—referred to us by NGO staff will be screened for eligibility. If eligible and interested in participating, they will undergo informed consent procedures. As part of this process, participants will be informed of all the potential risks and benefits to taking part in the study. Participants will be reminded that participation is voluntary, that they can decline to answer any questions they are not comfortable answering, they can leave the study at any point, and their decision to participate in the study will not impact their job. As part of signing the consent form, they will also consent to the Protection of Personal Information Act 4 of 2013.

3.5.2b CHW Baseline and Pre-Training Assessments

Baseline Assessment. Upon giving willing, informed consent, CHWs will complete a baseline assessment with study staff. The baseline assessment will consist of self-report questions around CHWs' demographic characteristics and job, personal mental health questions, questions around knowledge of HIV, TB, depression and substance use, and questions around stigma.

Pre-Treatment Assessment. Immediately before their training, participants will complete a pre-training assessment. At this visit, participants will be asked to answer the same self-report questionnaires and as they did at baseline (with the exception of demographic and job information, which will not be asked again). All CHWs will also complete a brief (~10 minutes) role-play vignette with a staff member who is minimally involved in delivering the training, which will be videotaped and later coded for stigma using the ENACT.

3.5.2c CHW Training

After the baseline assessment all groups will receive at least one dose of TAU. Based on the training time to which their cluster was randomized, CHWs will then be invited to participate in a training on mental health and substance use.

Clusters randomized to Training Time #1 will receive the training first (while the other training times continue to receive TAU), followed by Training Time #2 (while the final training time continues to receive TAU), and finally, Training Time #3.

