The training in the stepped-wedge trial will be the as the initial training, with minimal adaptations based on participant feedback (e.g., potentially an additional day, allocating more or less time to specific concepts, etc.). It will still be conducted in English, as all CHW trainings offered by the Western Cape Department of Health are required as part of the CHW certification occur in English. Roleplays will be conducted in English (training language) or isiXhosa (patients' language). Additionally, our training team consists of English, isiXhosa, and Afrikaans mother-tongue speakers; therefore, our team will be able to address questions and further explain concepts in these languages if needed.

3.5.2d CHW Post-Training Assessments

In addition to the Baseline and Pre-Treatment Assessments (which both occur before the training, and therefore, measure TAU), CHWs will also be required to complete two additional assessments after the training:

3-Month Follow-Up Assessment (3MFU): All participants will be invited to complete a follow-up assessment approximately 3-months after their training (3MFU). At this visit, participants will answer the same self-report questions they answered at the Pre-Training Assessment, answer additional questions about their perceived feasibility/acceptability of the training, and complete a roleplay for later ENACT coding.

6-Month Follow-Up Assessment (6MFU): All participants will also be invited to complete another follow-up assessment approximately 6-months after their training (6MFU). At this visit, participants will answer the same self-report questions they answered at the 3MFU and complete a roleplay for later ENACT coding. A subset of CHWs will also participate in semi-structured individual interviews in which they answer open-ended questions about their perceived feasibility/acceptability of the training.

3.5.2e Additional CHW Self-Report Measures

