4.3 Primary Preliminary Effectiveness Outcomes (Stepped-Wedge Trial Only)

4.3.1 –Stepped Wedge Trial

CHW Stigma. The primary measure of CHW stigma is the Social Distance Scale (SDS),^{20,43,44} a well-validated measure of stigma used to capture health-related stigma across conditions and has been recommended for assessing mental health stigma among healthcare providers. A total SDS score will be calculated to represent CHW stigma towards the target population at each timepoint, with high scores indicating greater desire for social distance. First, we will conduct descriptive analyses (e.g., mean, standard deviation) to summarize the CHW stigma, using the continuous SDS score. The data distribution will be assessed to see whether the underlying assumptions are met (e.g., normality). To account for the stepped wedge study design, we will fit a linear mixed model (LMM). This analytic approach will allow us to account for both random effects of the clinic and CHW, and fixed effects of time and the effect of the training. We will analyze the within- and between-group effects. Specifically, the within group effect will evaluate changes in stigma before and after receiving the training with CHWs from the same clinic,

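### The 86% / 96% power used to set N=60 is not delivered by the documented visit schedule under the usual codings of the required time effect

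*Combined protocol and SAP*

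**What the plan says.** Section 3.3.2a (Rationale for enrolment numbers) says N=60 came from power calculations for the SDS under a linear mixed model. It assumes "an intra-class correlation of 0.1 within clinic and 0.3 within person, with 60 CHWs", and concludes that "our study can achieve a power of 86% at a significance level of 0.05 and a CHW training effect of 0.63", with 96% at 0.75. It does not give the step length, the assessment months, the time term or the sidedness of the test.

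Section 3.2.2 describes three training times and about 20 CHWs per cluster. For the untrained condition the "timepoints are baseline assessment (t1) and pre-training assessment (t2"); for the trained condition the "additional timepoints are 3-month follow-up (t3) and 6-month follow-up (t4) after adjusting for individual random effect and time effect". Section 4.3.1 repeats that the model has "fixed effects of time and the effect of the training". Neither says whether time is visit or calendar month, categorical or linear.

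On timing, section 3.5.2b says: "Immediately before their training, participants will complete a pre-training assessment". Section 3.5.2d puts the follow-ups "approximately 3-months after their training (3MFU") and "approximately 6-months after their training (6MFU"). Section 3.5.2e says there is no immediate post-training assessment, only a further role-play on the last training day. Section 7 has a common baseline in month 3, training in months 5, 6 and 7 for the three groups, first follow-ups in printed months 9, 10 and 11, and second follow-ups in printed months 12, 13 and 14. No row is labelled month 8.

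**The concern.** A stepped wedge separates the training effect from secular change by comparing, at the same calendar time, clusters already trained with clusters still waiting. That needs assessments of both kinds at common times. Here, after baseline, each group is assessed only around its own training date, and the first SDS measurement after training comes about three months later. With one-month steps, the last group has had its pre-training assessment before the first group has its first follow-up.

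The primary effectiveness model may therefore be unable to separate training from time, or may do so only through an assumed shape for the time trend. The power that justified the sample size would then describe a different layout from the one documented.

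**Working it through.** **Inputs.** 60 CHWs in three clusters of 20 (section 3.2.2); effects 0.63 and 0.75, alpha 0.05, correlations 0.1 and 0.3 (section 3.3.2a). Assumptions: two-sided test, total variance 1, no dropout, no covariates, large-sample normal power. The within-person 0.3 can be read two ways: as the total within-person correlation (clinic 0.1, CHW 0.2, residual 0.7) or as additional to the clinic part (0.1, 0.3, 0.6). Ranges below run from the first reading to the second.

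**Method.** The SE of the training effect is the square root of its diagonal element in (Σ X′V⁻¹X)⁻¹, where X holds the time terms and the training indicator and V is the mixed-model covariance. Power = Φ(δ/SE − 1.96). Estimability is checked from the rank of X.

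**Step 1: the plan's own figure.** The stated power implies SE = 0.63/(1.96 + 1.080) = 0.207 and 0.75/(1.96 + 1.751) = 0.202. A complete wedge of three sequences and four periods, with every cluster assessed in every period, categorical time and components 0.1/0.2/0.7, gives SE 0.2006 and power 88.1% / 96.2%. A t reference with 58 df gives 87.1% / 95.7%. The stated figures are close to this layout, which the protocol does not describe. Omitting time altogether gives above 99%, so that does not explain them.

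**Step 2: categorical visit.** Training is 0 at t1 and t2 and 1 at t3 and t4 for every CHW, so the training column equals the t3 column plus the t4 column: 5 columns, rank 4. Step length and number of clinics do not enter.

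**Step 3: categorical month.** Untrained assessments fall in months 3, 5, 6 and 7. Trained ones fall in months 8–13 with follow-ups at +3/+6, or 9–14 as printed. The sets do not overlap, so the training column is the sum of the later month columns: 11 columns, rank 10 under either reading.

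**Step 4: smooth trends and coarser periods on the documented schedule.**

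| Time term | Follow-up months | SE | Power at 0.63 | Power at 0.75 |
|---|---|---|---|---|
| Linear month | +3/+6 (section 3.5.2d) | 0.235–0.218 | 76–82% | 89–93% |
| Linear month | as printed in section 7 | 0.267–0.247 | 66–72% | 80–86% |
| Linear visit | either | 0.242–0.224 | 74–80% | 87–92% |
| Cubic month | +3/+6 | 0.334–0.309 | 47–53% | 61–68% |
| Periods 3–8, 9–14 | +3/+6 | 0.218–0.202 | 82–88% | 93–96% |
| Periods 3–8, 9–14 | as printed | not estimable | – | – |
| Periods 2–5, 6–9, 10–13 | +3/+6 | 0.200–0.185 | 88–93% | 96–98% |
| Periods 3–6, 7–10, 11–14 | +3/+6 | 0.231–0.214 | 78–84% | 90–94% |

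For the first row: 0.63/0.2353 − 1.96 = 0.717, giving 76.3%; 0.63/0.2180 − 1.96 = 0.930, giving 82.4%. Six clinics of 10 change the linear-month figures by under 1 point.

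**Step 5: other calendars.** Two-month steps with linear month give 85–90% / 94–97%. Three-month steps, where trained and untrained assessments coincide in two months, give 83–88% / 94–96% with categorical month. Both are near the stated figures; neither is the section 7 calendar.

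**Step 6: the printed months.** For the first group, 9 − 5 = 4 and 12 − 5 = 7 months, against 3 and 6 in section 3.5.2d. Counting the rows consecutively restores 3 and 6, so the gap looks like a numbering slip or a lost row.

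**The case against.** The strongest reply is that the plan never commits to visit or month indicators. A reader might infer from steps 2 and 3 that any categorical time term makes the effect inestimable, or that the stated power cannot be reached on this calendar. The documents support neither inference. Six-month periods from baseline, with follow-ups at +3/+6, are full rank and give a range that includes 86% / 96%. That part of the reply stands.

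Its weight is limited. The six-month version works only because the first group's month-8 follow-up falls in the same period as the untrained assessments. Move it to month 9, as printed, and the effect is not estimable. Every such coding also assumes a flat trend within each period, and nothing in the plan specifies these periods.

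Other fair points: section 7 is headed as approximate and the clinics were still to be settled; the trial is a pilot of preliminary effectiveness; and the ranges above rest on assumptions of their own. With three clusters, a small-sample reference would lower power further, and covariates could move it. These are reasons not to treat any single figure here as the correct one. They do not rescue the stated figures, because the categorical-visit and linear-visit results do not depend on the calendar.

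**Conclusion.** The concern holds. Under categorical visit, and under categorical month on the section 7 calendar, the primary training effect is not estimable. Under a linear month trend the power is below that stated. With follow-ups at +3/+6 the shortfall is about 4–10 points at 0.63 (86 − 82.4 to 86 − 76.3) and 3–7 points at 0.75 (96 − 93.1 to 96 − 89.0). On the printed months it is about 14–20 and 10–16 points. These sizes assume 60 CHWs, a two-sided 0.05 test, clinic variance 0.1, CHW variance 0.2–0.3 and no dropout.

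The non-estimability results follow from the schedule alone and need no variance assumption. The power ranges are illustrative and depend on the time term.

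A reader might also infer that the power calculation contains an arithmetic error or that the trial needs more CHWs. The documents show neither. The figures are close to those of a complete wedge, and section 3.3.2a does not state the layout used. What is shown is a mismatch between the stated power and the documented schedule, in a pilot where a correct statement is what is needed.

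**What to change.** - **Section 3.3.2a:** restate the power for the schedule and time term that will be used in the primary SDS model. Give step length, assessment months, number of clusters, time coding and the meaning of the within-person 0.3. The ranges above need not be printed.
- **Section 4.3.1:** specify a time term under which the training effect is estimable: not categorical visit, and not categorical month on the section 7 calendar. State that the estimate then relies on the assumed shape of the time trend, because no trained and untrained assessments are concurrent.
- **Section 7:** if the calculation assumed longer steps or a complete wedge, correct the calendar to match. Reconcile the missing month 8 row with the 3- and 6-month follow-ups in section 3.5.2d.

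The cost is a rewritten paragraph, a sentence or two on the model and a corrected table. No extra CHWs or visits are needed. The price is a less favourable stated power and an explicit modelling assumption.

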1.2.2 Stepped-Wedge Pilot Trial

To further evaluate the implementation (feasibility, acceptability, fidelity) and preliminary effectiveness of this CHW training program to reduce CHW stigma towards depression and SU in order to promote re-engagement in TB/HIV care, we will conduct a Type 2, hybrid effectiveness-implementation trial.¹ This will be guided by Proctor's implementation model.² Using a stepped-wedge design with multiple NGO/clinic sites ($N = 60$ CHWs total), we will randomly allocate the timing of the CHW training (versus treatment as usual; TAU) over six months. The following multi-level outcomes will be evaluated:

- a. Feasibility, acceptability and fidelity of the CHW training (primary implementation outcomes). This will be assessed through both quantitative and qualitative methods so that qualitative data can add key context to quantitative findings and will include both CHWs and stakeholders (e.g., NGO leaders, policymakers focused on CHW training, supervisors of CHWs) to identify potential organizational barriers and facilitators to implementation of the training beyond the course of this study.
- b. CHW stigma towards depression and SU in TB/HIV patients (primary; effectiveness outcome)
- c. Patient re-engagement in TB/HIV care over six months via chart review (secondary effectiveness outcome)

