3.4.2. Stakeholder recruitment

NGO leaders, policy makers and other stakeholders (up to $n=28$) will also be recruited. These stakeholders will be recruited after referral from health system leadership. Additionally, stakeholders who participated in Phase 1 interviews may be re-enrolled to participate in these follow-up interviews. Trained study team

members will approach stakeholders, tell them about the study procedures, and ask if they would be interested in participating.

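### The stakeholder eligibility table in 3.3.2b, read literally, excludes stakeholders whom the protocol sets out to interview

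*Combined protocol and SAP*

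**What the plan says.** Section 3.3.2b (Stakeholder participants) plans up to 28 NGO leaders, policymakers and other stakeholders who work with the partner NGOs. Its rule is conjunctive: "To be eligible, stakeholders must meet all of the criteria in the below table". The three inclusion items are age 18 or over, "Be employed by or referred by a partner NGO that provides HIV/TB CHW services", and "Work with patients who have HIV and TB and struggling with depression or SU". The two exclusions are inability to consent or complete procedures in English or isiXhosa, and "Unable to complete training in English". The sentence after the rule says that people who took part in the formative work can be enrolled, and that prior participation is not required.

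Objective (a) in 1.2.2 names the people wanted: "stakeholders (e.g., NGO leaders, policymakers focused on CHW training, supervisors of CHWs". Section 3.5.2g plans interviews with NGO leadership staff, policymakers and others after the 6-month follow-up. On recruitment, 3.4.2 says: "These stakeholders will be recruited after referral from health system leadership". It adds that stakeholders from the Phase 1 interviews may be re-enrolled. Section 3.5.2f says that NGO leaders and stakeholders will be screened for eligibility before consent.

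**The concern.** The stakeholder interviews are meant to supply what CHWs cannot: the organisational and policy view of barriers, facilitators and longer-term sustainment (1.2.2 and 3.5.2g). Section 4.2 compares their themes with the CHW findings on feasibility and acceptability. A criterion written for front-line workers, applied with an all-criteria rule, pulls the sample towards people close to CHW practice and away from the perspectives the interviews are for.

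Because stakeholders are screened against this table, staff would face two poor options. They could turn away people whom the protocol names as intended participants, or they could enrol people who fail the written criteria. The second is a protocol violation, which 6.2.4 requires to be reported to the ethics committee within 7 days and 6.2.6 requires in the annual progress report to the sponsor.

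**Working it through.** No sample size, power figure or rate is involved, so the check compares text in three steps.

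**Step 1: the two eligibility tables for the stepped-wedge trial (3.3.2a and 3.3.2b).**

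| CHW table | Stakeholder table | Relation |
|---|---|---|
| Inclusion 1: age 18 or over | Inclusion 4 | Same |
| Inclusion 2: "Be employed as a CHW through a partner NGO that provides HIV/TB CHW services" | Inclusion 5: "Be employed by or referred by a partner NGO that provides HIV/TB CHW services" | Adapted |
| Inclusion 3: "Work with patients who have HIV and TB and struggling with depression or SU" | Inclusion 6 | Same words |
| Exclusion 1: consent or procedures in English or isiXhosa | Exclusion 1 | Same |
| Exclusion 2: "Unable to complete training in English" | Exclusion 2 | Same words |
| Exclusion 3: "Participated in the initial trial(s) of this training" | None | Dropped |

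Of the six CHW items, four carry over unchanged, one was adapted and one was dropped (4 + 1 + 1 = 6). The table was therefore partly adapted, but two of the unchanged items, inclusion 6 and exclusion 2, do not fit the stakeholder role. The stakeholder inclusion numbers even run on from the CHW list (4 to 6).

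**Step 2: apply the stakeholder table to the roles the protocol names.** Each row states its assumption about patient work and referral, because the documents do not give these by role.

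| Person | Inclusion 5 | Inclusion 6 | Result |
|---|---|---|---|
| CHW supervisor at a partner NGO, no own patient work | Met | Fails | Ineligible |
| Partner-NGO leader, no own patient work | Met | Fails | Ineligible |
| Policymaker referred by a partner NGO, no patient work | Met | Fails | Ineligible |
| Policymaker referred only by health-system leadership, no patient work | Fails | Fails | Ineligible |
| Non-NGO provider with such patients, referred only by health-system leadership | Fails | Met | Ineligible |
| Partner-NGO staff member who works with such patients | Met | Met | Eligible, subject to age and language |

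A CHW enrolled in the trial meets all the stakeholder criteria, since being employed as a CHW through a partner NGO satisfies inclusion 5. So the table does not separate the two groups, while it shuts out roles that objective (a) names.

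**Step 3: can the wording be read more loosely?** In the initial pilot, section 3.3.1a pairs the same patient-work requirement with an explicit alternative for people who supervise such CHWs. The authors thus gave supervision its own wording where they meant to include it. The stakeholder table has no such alternative, and none for leadership or policy roles.

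On exclusion 2, sections 3.5.2f, 3.5.2g and 3.6.1c describe only screening, consent and interviews for stakeholders. Since exclusion 1 accepts isiXhosa, a person who could be interviewed in isiXhosa can still be excluded over a training that they are not described as attending.

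**The case against.** The best defence is that the intent is plain. Sections 1.2.2, 3.3.2b, 3.4.2 and 3.5.2g all name leaders or policymakers, so sensible staff would enrol them. That makes this a drafting inconsistency rather than a chosen restriction, and I accept that description. It does not remove the need for a correction, because screening is done against the written table.

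The sentence on formative-work participants might be a separate route to eligibility. On a narrower reading it says only that earlier participation is no bar. Even on the generous reading it covers only those who took part before, and 3.3.2b does not limit recruitment to them.

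A reader might infer that every intended stakeholder is shut out, or that no policymaker could be interviewed. The documents do not support this. They do not define what working with patients means, do not say how many leaders or policymakers lack patient contact, and do not split the 28 by role. The timeline in section 7 mentions CHWs and providers among the interviewees, so some are patient-facing. An empty policymaker group is a worst case.

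Nor is recruitment solely through health-system leadership. NGO stakeholders from the formative work are also sought, and partner-NGO employees satisfy inclusion 5 whoever refers them. The two referral routes may overlap; the documents do not say. The English-training exclusion may also remove few people, since 3.5.1b describes English as the healthcare system's business language.

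Finally, it would be tempting to say that the primary implementation outcomes are compromised. They are not measured on stakeholders. Fidelity comes from CHW roleplays, feasibility from CHW attendance and a CHW subscale, and acceptability from a CHW subscale. Stakeholder themes are compared with these for context, and no threshold, estimate or test depends on them.

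**Conclusion.** The point stands as an internal contradiction that should be corrected. The table in 3.3.2b conflicts with the stakeholder population in 1.2.2, 3.3.2b and 3.5.2g and with the recruitment route in 3.4.2. Read literally, it makes two groups ineligible: leaders, policymakers and supervisors who do not themselves work with the specified patients, and non-NGO stakeholders referred only by health-system leadership.

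The number affected is unknown. It could lie anywhere from 0 to the cap of 28, depending on each person's patient contact and referral source. That some of the named roles lack patient contact is an assumption drawn from the nature of the roles; the documents neither state nor deny it.

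The consequence is limited to the qualitative stakeholder strand. The CHW quantitative measures, the SDS analysis and its power calculation are unaffected.

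**What to change.** Amend the stakeholder table in 3.3.2b as follows.

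- **Exclusion 2 (training in English):** delete it.
- **Inclusion 6:** replace it with a role criterion, for example: has a leadership, supervisory, policy or provider role in NGO-managed CHW services or in CHW training, and is not enrolled as a CHW participant in the stepped-wedge trial. The last clause is needed because the present table does not separate stakeholders from trial CHWs.
- **Inclusion 5:** let any one of three routes suffice: employment by or referral from a partner NGO, referral from health-system leadership, or participation in the Phase 1 interviews. This matches 3.4.2 and settles the status of formative-work participants.

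The cost is a one-table amendment, submitted to the ethics committee before it is implemented (6.2.2). It adds no procedures. In the section 7 timeline these interviews fall in months 13 to 15, at the end of the trial.
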